Observational Study Protocol

Versione n. 1.0, 23_May_2022 Firma del PI: [name]

Titolo dello studio

APOLLO 11, CONSORTIUM OF LUNG CANCER PATIENTS TREATED WITH INNOVATIVE THERAPIES: INTEGRATION OF REAL WORLD DATA AND TRANSLATIONAL RESEARCH

	BACKGROUND
Rational	Lung cancer is the leading cause of cancer-related mortality worldwide. The global
	incidence in 2018 was an estimated 2 million cases with 1.7 million deaths predicted
	(1). A 70% increase in the number of new cases of lung malignancy is expected over the
	next 2 decades (1). There are two major subtypes of lung cancer: small cell lung cancer
	(SCLC) and non-small cell lung cancer (NSCLC), accounting for approximately 15-20%
	and 80-85% of total cases, respectively (2). Within NSCLC, 45-65% is represented by
	adenocarcinomas, 15-25% by squamous cell carcinomas, 5% by large cell
	neuroendocrine carcinomas, and the remainder by "not otherwise specified" carcinomas
	(3). About 70% of patients with NSCLC, at the time of diagnosis, have advanced disease
	not amenable to surgical resection while SCLC is always considered a systemic disease
	(4). For several decades, cytotoxic chemotherapy has been the only treatment able to
	prolong survival in advanced patients with both SCLC and NSCLC. In recent years, in NSCLC, progress in better understanding of cell biology has led to the identification of
	specific genetic alterations, known as "driver" alterations, at the basis of tumorigenesis,
	including mutations of EGFR, KRAS, BRAF and MET, and rearrangements of ALK,
	ROS1, RET genes. The use of "target therapies" is now the treatment choice in this
	subgroup of patients. About 15% of NSCLC harbour somatic mutations in EGFR.
	Tyrosine kinase inhibitors (TKIs) such as gefitinib, erlotinib, and afatinib resulted in
	significantly improved progression-free survival (PFS) compared with standard
	chemotherapy and were initially indicated as first-line therapy (6-13). More recently,
	osimertinib, a 3rd generation drug, has reported, compared with other TKIs, a significant
	advantage in terms of PFS and OS and has become the new first-line standard (14). In
	light of its superiority over chemotherapy in the AURA3 trial (15), osimertinib also
	represents the second-line standard in patients with T790M-mediated acquired resistance
	to first-line therapy with first- and second-generation EGFR-TKIs (approximately 60%
	of cases). The ALK gene is shown to be rearranged in 5% of NSCLC cases. The first
	agent approved for ALK-positive NSCLC was crizotinib. Following initial disease
	control almost all patients inevitably develop resistance within approximately 12 months
	with disease progression predominantly in the brain (16). Therefore, the development of
	next-generation ALK inhibitors has been encouraged. To date, ceritinib, alectinib,
	brigatinib and lorlatinib have received approval from the Food and Drug Administration
	(FDA) and/or the European Medicines Agency (EMA), and the Agenzia Italiana del
	Farmaco (AIFA), for the treatment of ALK rearranged NSCLC demonstrating an anhanced ability to papetrate through the blood brain barrier. Moreover, in angoing
	enhanced ability to penetrate through the blood-brain barrier. Moreover, in ongoing clinical trials othe novel ALK-TKIs have provided promising preliminary data in terms
	of both clinical activity and safety (17).
	The advent of immunotherapy has further changed the therapeutic landscape in both
	NSCLC without "driver" alteration (NSCLC-WT) and SCLC. This is a treatment
	and blie hand a makilization of the immune matery in and below. This is a field fille

NSCLC without "driver" alteration (NSCLC-WT) and SCLC. This is a treatment modality based on mobilization of the immune system in order to recognize and destroy tumor cells. Immune Checkpoint Inhibitors (ICIs), have been developed with the intent to act on those pathways of "self-tolerance" used by tumors to escape recognition and then destruction by the immune system. By blocking these inhibitory pathways, which physiologically control the immune response, they reactivate and sustain the immune system against tumor cells (18). In particular, cytotoxic T-lymphocyte-associated-4 (CTLA-4) programmed cell death protein 1 (PD-1) are receptors expressed on T cells that, by interacting with CD80/CD86 (19) and programmed cell death protein 1 (PD-L1) or PD-L2 ligands, respectively (20), are able to promote and foster immune evasion by tumor cells. Several ICIs, capable of blocking PD-1/PD-L1 and CTLA-4 inhibitory

Objectives	OBJECTIVES
and clinical	Primary objectives:
and clinical relevance	 To create a network of Italian Lung Cancer Centers (APOLLO 11 Consortium) through: The development of a National Real World distributed database assets for lung cancer patients (NSCLC and SCLC) treated with INNOVATIVE THERAPIES (immunotherapy, target therapy and next generation treatments). Building the consortium, harmonizing all the relevant ethical, legal, and data protection issues among centers. The development of a National "virtual multilevel biobank" in lung cancer patients through the creation of real local biobanks stored in each participating center. The set-up and harmonization of the operative procedures for collection, storage and shipment of all the biological specimens
	 foreseen. 2. To identify a specific factor or combinations of factors (i.e. mutations, transcript abundances, protein levels and immunological markers) influencing response, progression/hyperprogression, treatment resistance, survivals in lung cancer patients (NSCLC and SCLC). In particular in the first phase, we will focus our analysis in: Integrating retrospective and prospective multisource data collection of advanced NSCLC already treated or candidate to receive ICIs-based therapy to assist the creation of a predictive artificial intelligence (AI) model to improve response prediction, ultimately leading to better cancer patients survival and their Quality of Life. Characterizing the immune circulating profile by single cell analysis, FACS analysis, and TCR sequencing in order to correlate these variables with clinical outcome of NSCLC patients receiving first line ICIs treatment feeding the predictive machine learning algorithms. Collecting all the available ICIs baseline CT scans from retrospective and prospective aNSCLC patients treated with ICIs to create and validate a radiomic signature and use its value to refine the predictive algorithms. Further scientific objectives of APOLLO 11: To evaluate the association of data on genomics, tumoural and immunological microenvironment with clinical and pathological features of lung cancer (NSCLC and SCLC) treated with innovative therapies (immunotherapy, target-therapies and next-generation therapies).

	 To identify how specific factors or combinations of factors (tumoral microenviromental and immunological markers) may influence response progression, atypical response (hyperprogression or pseudoprogression) and treatment resistance in lung cancer (NSCLC and SCLC). To evaluate the prognostic role of these factors or combinations of factors in lung cancer (NSCLC and SCLC). To assess possible changes over time of specific factors or combinations or factors (gene, biomolecular and immunological markers) in relation to the clinical evolution of the disease. To specifically assess the role of metabolism in influencing tumour biology the biology of the anti-tumour immune response and the activity of cancer therapies. To evaluate the possible impact of clinical characteristics, comorbidities and concomitant therapies on oncological outcomes To develop prognostic/predictive models of response/resistance to
	innovative treatments analyzing "big data" through artificial intelligence methods such as machine learning and deep learning in order to tailou treatments for patients with lung cancer and guide decision-making processes.
	8. To use XAI approach to study decision-making systems (such as traditional AI and ML methodologies), with the aim of making them more interpretable, transparent, explainable, and reliable for clinicians by unfolding the black box of the AI algorithms.
	 To compare mutational and gene expression profiles identified in tumout tissue with those identified in peripheral blood. To identify factors or combinations of factors predictive of response resistance, disease progression in blood, urine, faeces and/or any other available biological material in lung cancer (NSCLC and SCLC).
	 To define the immunological mechanisms underlying immunorelated toxicities or toxicities derived from target therapies and possible biomarkers associated with their development and clinical course. To define the mechanisms of secondary resistance to specific treatments
	 used in lung cancer e.g., in patients with EGFR, ALK, ROS1, RET, BRAF HER2, KRAS, MET exon skipping 14 and other possible driver alterations and their relative driver TKIs. 13. To identify new potential therapeutic targets at the level of any biological
	material. 14. To identify the association between meta-genomic profiles on stool, patients immune phenotype and cancer outcome.
Firstly,	CAL RELEVANCE creating an Italian network of hospitals with expertise in the treatment of d LC and facilitating the integration of real-world data and biological samples

from multiple centers, in line with the credo "union is strength", will avoid unnecessary dispersion of data from single institutions that are often inconclusive, due to the limit sample number. This real-world data collection will also help to understand real-world outcomes, which frequently are not the same compared to results upcoming from clinical trials. With the advent of several innovative therapies (target, ICIs and next-generation therapies), there is an increasing attention towards mechanisms potentially involved in tumor escape in both NSCLC and SCLC. APOLLO 11 network aims to identify and combine different types of markers (clinical, radiologic, genetic, molecular and immunological) in different histologies (NSCLC and SCLC)capable of predicting response to therapy, toxicity, relapse after curative intervention or associated with primary and acquired resistance. Moreover, the identification of gene expression, biomolecular and immunological profiles may allow an increased personalization of lung cancer (NSCLC and SCLC) treatment. The aforementioned analyses/activities will be carried out on the collected data in the local databases. Moreover, the sample collected and stored in each local biobank will be shared and used to achieve the primary objectives. Moreover, biological samples will be accessible over time as soon as dedicated funds are available to address the specific objectives described above and future research in the light of the evolution of scientific evidence.

Study population	 Patients affected by lung cancer will be enrolled according to the following inclusion criteria: 1. Provision of signed and dated written informed consent, when applicable, by the patient or legally acceptable representative prior to any mandatory study-specific procedures, sampling, and analyses; 	
	2. Patients must be \geq 18 years of age at the time of signing the informed consent;	
	3. Histologically or cytologically confirmed lung cancer (NSCLC or SCLC) at any stage (I-IV) candidate to receive or already treated with innovative therapies (ICIs, target therapies and next generation therapies).	
	Patients must not enter the study if any of the following exclusion criteria are fulfilled:	
	 Patients who are or will be taking other unapproved antineoplastic therapies concurrently are not eligible. 	
	2. Patients who have not received an oncological systemic innovative therapy at any setting	
	3. Patients received only local treatments (e.g., only surgery, or only radiotherapy)	
	4. Patients who received only standard chemotherapy are excluded.	
	5. Patients who received treatment therapies before 2010 are excluded.	

Methods and study design	This is a retrospective/prospective multicenter observational study that will enroll lung cancer patients (NSCLC and SCLC) treated with at least one innovative systemic treatment. DATA and MATERIAL COLLECTION (Figure 1)
	Real world data collection on the local databases (REDcap) Retrospective phase: all the involved centers will participate in the collection of clinical data that will be stored in the local database of each Center. This phase involves the collection of "real world" available jeopardized data (e.g., demographic, epidemiological, clinical, biochemical, biological, radiological including also data of treatments performed, survival, and toxicity outcomes) related to cases of lung cancer (NSCLC stage I - IV and SCLC-LD and ED) treated with innovative therapy (e.g., target therapy, immunotherapy and next generation therapies) since January 2010 at the moment of ethical committee approval if the patients have already started the innovative therapy.
	Prospective phase: each patient with new diagnosis of lung cancer (NSCLC stage I - IV and SCLC-LD and ED) candidate to receive an innovative therapy and able to sign the informed consent to the processing of personal data can be enrolled in the prospective phase. In this phase homogenized data will be collected from the date of the committee approval. The data will be entered into the local REDCAP database.
	Imaging collection: For both retrospectively and prospectively enrolled patients, CT, PET and MRI scans will be performed as per standard of care, locally stored and shared, with the same code assigned during enrollment, to achieve the described objectives as detailed in the data management plan. The collection of these images will be performed at each innovative treatment at first radiologic evaluation, best response and radiological progression.
	Radiomics analysis: the first analysis will start on ICIs baseline CT scans of aNSCLC- IO cohort. In the retrospective phase in around 1000 patients and prospectively in around 200 patients. The CT scans from the participating sites will be de-identified in accordance with GDPR standards and encrypted prior to transmission to the central server for Radiomics analysis. A dedicated radiologist will analyze CT images and 3D tumour targets volume delineation will be manually determined for each patient and image segmentation will be performed. The main clusters of patients will be related with other collected parameters and the generated radiomics signature will be validated and then integrated with AI models.
	Biological samples collection for translational research The study foresees the annotation of samples already available for standard of care (i.e. FFPE tumor tissue) for retrospective enrolled patients in dedicated CRF. In case of

previous other samples collection (e.g., blood, feces etc) in this setting it is possible to record retrospectively these samples in the dedicated CRF.

The study foresees the collection, preservation and annotations of biological samples (peripheral blood, stool, urine, saliva as per protocol and, when available, tumor tissue collected as per standard of care) for prospective enrolled patients.

Each biological sample collected per protocol will be identified with the same code assigned to the patient when enrolled, with a label reporting also date of collection, and type of specimens. Moreover, these information and storage references will be entered into dedicated CRF.

Tissue collection

For both retrospective and prospective enrolled patients, cyto-histological tumor tissue collected for diagnostic purposes and during an innovative treatment per **standard of care**, will be annotated in the "virtual biobank" dedicated CRF. Two different types of storage are foreseen: 1) FFPE tissue sample 2) Frozen tissue, whenever possible.

[figure not shown]
Blood, urine, saliva, stool Samples Collection

For patients enrolled in the retrospective phase no blood specimens will be collected if the patients have already started the innovative therapy. A patient enrolled in the retrospective phase, could be also enrolled in the prospective phase, if he will start a subsequent innovative treatment. The same code patient will be assigned.

For patients enrolled in prospective phase, **blood**, **urine**, **saliva**, **stool** samples will be collected during the patient's appointments and therapies already scheduled on site at different timepoints for each innovative treatment (when more than one innovative therapy is foreseen for a single patient): 1) baseline, when treatment starts, 2) after the first cycle, 3) at the first radiological evaluation and 4) at evidence of progressive disease.

In particular, a total amount of 32 ml peripheral blood will be collected to obtain the following biological specimens for each timepoint.

Details for pre-analytical procedures are stated in detail in the **laboratory manual** of APOLLO 11 biobank.

Sample size and statistical analysis	Since the aim of the project is to identify prognostic/predictive factors of response, progression or resistance to treatment, for which incidence and prevalence data are not available to date, and in light of the multicenter participation in the study, the total number of patients who can be enrolled cannot be defined at present. About 48 IRCCS, general and academic hospitals from different Italian Regions will be involved in this study The study cohort for the first analysis will consist of around 1000 retrospective and 200 prospective aNSCLC-IO cases. The primary objective of this part is to compare the predictive accuracy of ML/DL methods (created using multisource data) with current validated biomarkers (e.g., PD-L1 or available scores). The study will have at least 85% power to detect a 0.1 increase in predictive accuracy as measured by the area under the ROC curve (AUC), assuming an AUC for validated biomarker alone of at least 0.6, using a one-sided z-test at a significance level of 0,050. The data are assumed to be discrete (rating scale) responses.
Informed consent	During the visit, after adequate information, the patient may sign an informed consent form, in accordance with the provisions of the regulations set out in Legislative Decree of 01 March 2012 no. 85, OJ General Series no. 72 of 26-3-2012, for the prospective collection of clinical data and conservation of biological samples. As it is impossible to ask for consent to process data from patients entered retrospectively, for ethical-administrative reasons, the study falls within the scope and purposes specified by the Guarantor for the Protection of Personal Data (General authorization to process genetic data - 15 December 2016 - Official Gazette no. 303 of 29 December 2016).

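### Exclusion criterion 2, judged at entry for both phases, literally bars the not-yet-treated candidates whom inclusion criterion 3 and the prospective phase admit

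*Protocol*

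**What the plan says.** All eligibility rules stand in the Protocol's Study population section, in one inclusion list and one exclusion list.

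- **Scope.** The lists are not split by phase. Inclusion criterion 1 reads "Provision of signed and dated written informed consent, when applicable", which fits a list meant for prospective patients, who can consent, and for retrospective patients, who are entered without consent.
- **Time of assessment.** The exclusion list opens with "Patients must not enter the study if any of the following" criteria is met, so the criteria are judged at entry.
- **Inclusion criterion 3** admits patients who are "candidate to receive or already treated with innovative therapies (ICIs, target therapies and next generation therapies").
- **Exclusion criterion 2** bars "Patients who have not received an oncological systemic innovative therapy at any setting".
- **Exclusion criterion 3** bars "Patients received only local treatments (e.g., only surgery, or only radiotherapy"). Exclusion criterion 4 does the same for patients whose treatment was standard chemotherapy alone.
- **Prospective phase** (Methods and study design): open to newly diagnosed patients who are candidates for an innovative therapy and can consent. Their first blood sample is due at the start of that treatment.
- **Objectives.** The first-phase data collection covers patients "already treated or candidate to receive ICIs-based therapy". The immune-profile objective concerns the "clinical outcome of NSCLC patients receiving first line ICIs treatment".

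**The concern.** Inclusion criterion 3, the first-phase objective and the prospective-phase definition all admit patients whose innovative therapy has not begun. Exclusion criterion 2 is written in the past tense and applied at entry, so it turns those patients away unless they had an innovative therapy earlier.

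What is at stake is the immune-profile objective in first-line immunotherapy. Under the sample collection section, retrospective patients who have already started therapy give no blood, so baseline blood collected under the protocol comes from prospective patients. A site that followed exclusion 2 to the letter would refuse first-line patients with no earlier innovative therapy, and its prospective intake would be mainly patients moving to a subsequent innovative treatment. About 48 hospitals are to use this list, and nothing in it tells them which of the two criteria prevails.

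**Working it through.** The protocol gives no figure to reproduce here. The check is logical: take the patient types the protocol describes and apply each criterion at entry, as the lead-in requires.

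| Patient at entry | Inclusion 3 | Exclusion 2 | Exclusions 3 and 4 | Result |
|---|---|---|---|---|
| A. Newly diagnosed, no treatment yet, candidate for first-line immunotherapy | met (candidate) | met (none received) | not met (nothing received) | eligible and excluded |
| B. Candidate, past treatment local only | met (candidate) | met | exclusion 3 met | eligible and excluded |
| C. Candidate, past treatment standard chemotherapy only | met (candidate) | met | exclusion 4 met | eligible and excluded |
| D. Retrospective patient, innovative therapy already started | met (treated) | not met | not met | eligible |
| E. Previously treated patient starting a subsequent innovative therapy | met | not met | not met | eligible |

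1. The conflict lies with the candidate half of inclusion 3 (rows A to C). The already-treated half (row D) is consistent.
2. Exclusions 3 and 4 exclude nobody beyond exclusion 2. A patient who has had only local treatment or only standard chemotherapy has received no innovative therapy and already meets exclusion 2. They do need the same repair, because correcting exclusion 2 alone would leave rows B and C in conflict.
3. Timing does not remove the conflict. Inclusion 1 puts consent before any study-specific procedure or sampling, and the first prospective sample is taken when treatment starts. Entry therefore comes before that sample. No passage says that exclusion 2 is judged later or in one phase only.
4. The tense matters. Exclusion 1 in the same list mentions future treatment: "Patients who are or will be taking other unapproved antineoplastic therapies concurrently are not eligible". Exclusion 2 has no such term. Its closing words about setting widen the circumstances in which therapy counts, not the time.
5. Row E shows that the prospective phase would not be emptied. The sample collection section lets a retrospective patient join the prospective phase when a further innovative treatment begins.

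**Numbers affected.** The first analysis plans around 1000 retrospective and 200 prospective cases. The retrospective cases are row D and are untouched. The protocol does not say how the 200 divide between rows A to C and row E, so the affected share cannot be derived.

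**The case against.** The strongest reply is that the intent is clear. Read together, exclusions 2 to 4 look like one scope limit: local treatment only, chemotherapy only, or no innovative therapy at all. The prospective-phase definition tells a site plainly whom to enrol, and a literal reading of exclusion 2 would defeat most of that phase. This largely stands, and it makes the point a drafting defect rather than a flaw in the design. It does not remove the contradiction, because no passage states the intended meaning and the list is the text a site screens against.

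Three stronger readings are tempting, and the documents do not support them.

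- **The whole prospective cohort would be lost.** A reader might take 200/(1000 + 200) = 16.7% of the first analysis as the loss. That figure is simply all of the prospective cases. It assumes that every site reads the rule literally and that none of the 200 had an earlier innovative therapy. The documents establish neither, and they expressly let previously treated patients in.
- **The immune-profile objective would have no blood.** The protocol also lets centres record samples of retrospective patients, including blood, that already exist. The narrower statement holds: baseline blood collected under the protocol comes from the prospective phase.
- **The design sentence is wrong as well.** Methods and study design describes the population as patients treated with one or more innovative systemic therapies. That wording fixes no time, covers patients whose treatment starts on study, and need not change. If anything it favours the benign reading of exclusion 2.

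**Conclusion.** The contradiction is certain on the text. Under one entry-time list for both phases, exclusion 2 bars candidates with no earlier innovative therapy, while inclusion 3 and the prospective-phase definition admit them. Exclusions 3 and 4 repeat the conflict for the two subgroups they name.

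The consequence is conditional. It arises only if sites follow exclusion 2 literally, and the documents do not show that they will. In that case the loss falls on first-line immunotherapy patients without earlier innovative therapy. Its size cannot be determined from the documents, and nothing is claimed about the stated power. The point should be fixed because an eligibility rule is wrong as written, it bears on the samples for a stated objective, and the correction is simple.

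**What to change.** Reconcile the passages in the Study population section in one of two ways.

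1. State that exclusions 2 to 4 apply only to the retrospective phase.
2. Reword exclusions 2 to 4 so that they exclude patients who have neither received nor are candidates to receive an innovative systemic therapy. This also covers patients with local treatment only or standard chemotherapy only. It is the complement of the treatment clause in inclusion 3, so it adds no new restriction.

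If exclusion 2 was also meant to deal with candidates who enrol and then never start an innovative therapy, neither option does so. That purpose would need its own sentence.

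The cost is a wording amendment to three criteria. It adds no patients, samples or procedures.

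### Does the first analysis, run only in ICI-treated patients and without a comparator, claim more about choosing treatment than an AUC gain can show?

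*Protocol*

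**What the plan says.** The section on sample size and statistical analysis gives the project's general aim: "Since the aim of the project is to identify prognostic/predictive factors of response, progression or resistance to treatment". It then narrows to one analysis: "The study cohort for the first analysis will consist of around 1000 retrospective and 200 prospective aNSCLC-IO cases". The stated objective of that part is to see whether models built on multisource data discriminate better than PD-L1 or available scores. The section claims at least 85% power for a gain of 0.1 in AUC, from a biomarker AUC of at least 0.6, with a one-sided z-test at 0.05.

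Primary objective 2 describes the first-phase work as data collection in "advanced NSCLC already treated or candidate to receive ICIs-based therapy to assist the creation of a predictive artificial intelligence (AI) model to improve response prediction". The same sentence adds the hope of "model to improve response prediction, ultimately leading to better cancer patients survival and their Quality of Life".

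Under a separate heading, the further scientific objectives include (seventh by position) prognostic or predictive models of response and resistance to innovative treatments, meant to help tailor "treatments for patients with lung cancer and guide decision-making processes".

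On eligibility, exclusion criterion 4 reads "Patients who received only standard chemotherapy are excluded". The design section says that the study enrols "cancer patients (NSCLC and SCLC) treated with at least one innovative systemic treatment".

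**The concern.** A marker is prognostic if it separates good from poor outcome whatever the treatment. It is predictive in the treatment-selection sense only if the benefit of one treatment over another varies with the marker. The second property needs patients on at least two treatments and a marker-by-treatment contrast. Here every patient in the powered analysis receives an ICI-based regimen, chemotherapy-only patients are outside the study, and no such contrast is described. The Protocol also joins the words prognostic and predictive with a slash, speaks of tailoring treatment, and links the first-phase model to better survival.

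Read together, these could suggest that a significant AUC gain would be offered as evidence of who should receive an ICI rather than something else. A purely prognostic score could then steer treatment decisions on which it carries no information.

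**Working it through.** **1. The stated power.** Inputs from the sample size section: AUC 0.60 against 0.70, one-sided 0.05, about 1000 + 200 = 1200 patients. The responder share and the correlation between the two AUCs are not given. They are assumed here as 0.2 to 0.5 and 0 to 0.6.

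The Hanley-McNeil variance of an AUC *A* with n1 responders and n0 non-responders is [A(1−A) + (n1−1)(Q1−A²) + (n0−1)(Q2−A²)] / (n1·n0), where Q1 = A/(2−A) and Q2 = 2A²/(1+A). The least favourable setting is share 0.2 (n1 = 240, n0 = 960) with correlation 0:

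- A = 0.60: (0.24 + 239 × 0.0686 + 959 × 0.0900) / 230400 = 0.000447
- A = 0.70: (0.21 + 239 × 0.0485 + 959 × 0.0865) / 230400 = 0.000411
- Standard error under the null: √(2 × 0.000447) = 0.0299
- Standard error under the alternative: √(0.000447 + 0.000411) = 0.0293
- Power: Φ[(0.1 − 1.645 × 0.0299) / 0.0293] = Φ(1.74) = 0.959

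The Obuchowski rating-scale variance gives 0.967 at the same setting, and every other setting gives more. So at least 85% holds as a lower bound when all 1200 patients enter the comparison. With the 200 prospective patients alone, power would be 0.39 to 0.89. Which patients test the model is a different question and does not bear on this one.

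**2. What an AUC under one treatment can show.** Assume an equal-variance binormal score, with d = √2 × Φ⁻¹(0.70) = 0.742. The overall response rate is also assumed.

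| Assumed response | Bottom third | Middle third | Top third | Top minus bottom |
|---|---|---|---|---|
| 20% | 8.8% | 17.6% | 33.6% | 24.7 points (from unrounded values) |
| 30% | 14.7% | 27.8% | 47.4% | 32.7 points |
| 45% | 25.9% | 44.3% | 64.7% | 38.8 points |

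- Case A: within each third, patients would respond to another treatment exactly as they do to ICI. The benefit of ICI is 0 in every third, so the difference in benefit between top and bottom is 0.
- Case B: response to the other treatment is the same in all thirds. It cancels from the difference, so the difference in benefit equals the ICI gradient, for example 47.4 − 14.7 = 32.7 points.

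The ICI data, the AUCs and the test result are the same in A and B, because no outcome under another treatment enters the test. The statistical principle is therefore right. The figures illustrate it; they do not measure anything in this Protocol.

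**3. Whether the Protocol draws the stronger conclusion.** Setting the places side by side:

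- The cohort of the first analysis is restricted to ICI-treated advanced NSCLC.
- The first-phase model is restricted to patients who had, or are candidates for, ICI-based therapy, and its purpose is to predict response.
- The powered comparison is between two scores, and what it measures is discrimination.
- The tailoring aim stands under a different heading, concerns innovative treatments in general, and is not linked by any sentence to the first analysis or its AUC result.

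The conclusion is thus limited by the text itself to outcome under ICI. The inference from AUC gain to treatment choice has to be supplied by the reader.

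**The case for a change.** The strongest contrary case is this. Better survival can follow from a model only if the model changes management, so the first phase is given a purpose beyond describing outcome. This is the only analysis with a stated power, and so the obvious support for a later tailoring claim. Excluding chemotherapy-only patients also means that further enrolment does not by itself supply that comparator. Two sentences of caution would cost nothing.

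Part of this stands. The wording is loose, the statistical distinction is real, and a tailoring claim would need more than this AUC comparison. But the survival phrase states a long-term hope (the Protocol says ultimately) and is not an inference from the test. Predictive is used elsewhere in the Protocol in its ordinary sense of forecasting outcome, as in predictive accuracy, and guiding decisions need not mean ICI against another drug. Criterion 4 is a scope choice for a consortium on innovative therapies. A comparator source or an interaction model for a further objective is detail that a statistical analysis plan, not shown here, may hold. The cautionary sentences would alter no analysis, sample size or stated conclusion.

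**Conclusion.** The concern does not hold. An AUC gain of 0.1 among ICI-treated patients fits a difference in treatment benefit of 0 points as well as one of 32.7 points (24.7 to 38.8 over assumed response rates of 20% to 45%). The Protocol does not claim otherwise. It confines the first analysis to predicting response in ICI-treated advanced NSCLC and lists treatment tailoring as a separate, further objective. If the plan is followed as written, the powered comparison and its conclusion stay valid, and the stated power is met as a lower bound (0.959 at the least favourable assumptions with all 1200 patients). This rests on reading the objectives as they are arranged in the Protocol. It would change if a report presented the AUC result as evidence for choosing between treatments.
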